8.1. Treatment-Emergent Adverse Events

The proportion of subjects with treatment-emergent adverse events (TEAEs) will be tabulated by treatment group and presented by MedDRA Preferred Terms within System Organ Class. The number and percent of subjects with treatment emergent adverse events, premature discontinuations due to adverse event, adverse events classified by their highest relationship to study drug, and adverse events classified by their maximum severity, will be summarized by MedDRA preferred term. A summary of all serious adverse events by treatment group will also be prepared.

A summary of the incidence of serious adverse events (SAEs) will be presented by MedDRA Preferred Terms within System Organ Class, and by treatment group.

8.2. Concomitant Medications

The use of concomitant medications will be listed.

8.3. Vital Signs

Vital sign data (systolic blood pressure, diastolic blood pressure, pulse, respiration rate, temperature, and body weight) will be summarized by treatment group and by visit, including mean changes from baseline.

8.4. Clinical Laboratory Results

Central clinical laboratory data will be summarized by treatment group and laboratory parameter, showing the proportion of subjects with abnormal values.

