5. STUDY ENTRY CRITERIA

5.1. Inclusion Criteria

Subjects must meet all of the following criteria to be considered for participation in this study.

- 1. Subject is able to comprehend and is willing to sign an informed consent/assent for participation in this study.
- 2. Male or female ≥ 8 years old.
- 3. Subject has a clinical diagnosis of common warts.
- 4. Subject has up to 1 Target Wart and up to 3 additional Non-Target Warts located on the trunk or extremities. The identified Target and Non-Target Warts must meet the requirements as defined below:
 - a. Each wart must have a longest axis that is \ge 3mm and \le 8 mm and have a thickness of \le 3mm
 - b. Each wart must be a discrete lesion
 - c. Each wart must be present for at least 4 weeks
 - d. Not be covered with hair which, in the investigator's opinion, would interfere with the study medication treatment or the study evaluations
 - e. Not be in an intertriginous fold
 - f. Be the only common wart present when the circular cutout template is centered over the wart
- 5. The Target and Non-Target Warts must have a $PWA \ge 2$
- 6. Subject chemistry and complete blood count results are within normal limits. If any of the laboratory values are outside normal range, the treating investigator must assess the value/s as NOT clinically significant and document this in the subject's medical chart in order for the subject to be eligible for randomization.
- 7. Women of childbearing potential (WOCBP) must have a negative urine pregnancy test within 14 days of the first application of study drug and agree to use an active method of birth control for the duration of the study.
- 8. Subject is non-pregnant and non-lactating.

- 9. Subject is in good general health and free of any known disease state or physical condition which, in the investigator's opinion, might impair the evaluation of any Target and Non-Target Warts or which exposes the subject to an unacceptable risk by study participation.
- 10. Subject is willing and able to follow all study instructions and to attend all study visits.

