9.3. Clinical laboratory sampling

Non-fasting blood samples for clinical laboratory analysis will be collected by a qualified staff member at Visit 1, Visit 9 and Visit 13. Approximately 7.5 mL of blood will be collected for each chemistry sample and 3 ml of blood will be collected for the complete blood count (CBC). These blood samples will be sent to a central laboratory for analysis. Refer to the study specific laboratory manual for instructions regarding handling of the blood samples and shipping instructions.

The following tests, at a minimum, will be conducted:

Chemistry Panel	Complete Blood Count	
Albumin	Hematocrit	
Alkaline phosphatase	Hemoglobin	
Alanine aminotransferase (ALT)	Platelet count	
Aspartate aminotransferase (AST)	Red blood cell morphology	
Blood urea nitrogen (BUN)	Red blood cell count	
Bicarbonate	White blood cell count	
Calcium	White blood cell differential	
Chloride	% & absolute	

Page 37 of 53 Amendment 2 Version 3 Date: 05 December 2017

- Creatinine Glucose Lactate dehydrogenase (LDH) Phosphorus Potassium Sodium Total bilirubin Total protein Uric acid
- Basophils Eosinophils Lymphocytes Monocytes Neutrophils

The results of the clinical laboratory tests will be reported on the central laboratory's standard reports. These laboratory results will be sent to the investigator via fax. The investigator must review all laboratory reports in a timely manner and note NCS or CS to define the clinical relevance of any result that is outside the normal range for the laboratory. The investigator must date and initial every laboratory report.

The investigator must review the Visit 1 laboratory results for all the measured analytes for each subject prior to Visit 2. The subject must not be randomized at Visit 2 if any of the Visit 1 results are outside normal range for the laboratory AND, in the opinion of the investigator, CS.

The investigator must report all laboratory results that are BOTH outside the normal range for the laboratory AND, in the opinion of the investigator, CS as medical history if found prior to the first study medication treatment or as an AE if found after the first study medication treatment begins.

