12.3. Statistical Analysis of Safety Data

Descriptive statistics will be calculated on the safety parameters using the ITT population. The proportion of subjects with treatment-emergent adverse events will be tabulated and presented by treatment and Medical Dictionary for Regulatory Activities (MedDRA) System Organ Class. Vital signs, LSR scores and clinically relevant abnormal laboratory results will also be tabulated and presented by study medication. No inferential testing will be performed.

Data from all randomized subjects will be presented and summarized. Safety summaries by study medication group will include listings by study medication of adverse events incidences within each MedDRA System Organ Class, and changes from pre-application values in vital signs. Adverse event summaries will be presented by study medication showing the proportion of subjects experiencing adverse events, both overall and by MedDRA System Organ Class.

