7.5. Treatment Compliance

Study medication use and accountability will be presented in a listing. Overall study medication use will be summarized by treatment group.

8. **PRESENTATIONS OF SAFETY INFORMATION**

Descriptive statistics by treatment group will be calculated on the safety parameters collected on or after Visit 3 using the Safety Population, defined as subjects who received at least one application of study medication. Safety summaries will include listings of clinical laboratory values and abnormal values, adverse events incidences within each Medical Dictionary for Regulatory Activities (MedDRA) System Organ Class, and changes from pre-dose values in vital signs. Adverse event summaries will be presented showing the proportion of patients experiencing adverse events, both overall and by MedDRA System Organ Class.

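### The laboratory tables in SAP 8.4 do not separate newly abnormal subjects from those already abnormal at Visit 1; a shift table would do so cheaply

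*SAP*

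**What the plan says.** SAP 8.4 is one sentence. Central laboratory data are summarised by treatment group and parameter, "showing the proportion of subjects with abnormal values". It names no visit, no direction (low or high), no change from baseline and no rule for what counts as new. The titles of Tables 14.3.4.1 (chemistry) and 14.3.4.2 (hematology) refer only to results outside the normal range. For vital signs, by contrast, SAP 8.3 asks for summaries by visit, "including mean changes from baseline".

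Out-of-range values are allowed at entry. Inclusion criterion 6 (Protocol 5.1) says: "If any of the laboratory values are outside normal range, the treating investigator must assess the value/s as NOT clinically significant". Protocol 9.3 sets the matching bar: "The subject must not be randomized at Visit 2 if any of the Visit 1 results are outside normal range for the laboratory AND" are also, in the investigator's opinion, clinically significant. The same section states that "Non-fasting blood samples for clinical laboratory analysis will be collected", and that samples "will be collected by a qualified staff member at Visit 1, Visit 9 and Visit 13". Visit 1 is thus the only scheduled pre-treatment sample.

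Three other provisions bear on the point:
- The opening of SAP Section 8 limits safety statistics to "safety parameters collected on or after Visit 3 using the Safety Population".
- SAP 7.4 includes laboratory evaluations in the baseline summary by treatment group.
- Protocol 12.3 states that "clinically relevant abnormal laboratory results will also be tabulated", and SAP 9.2 repeats this.

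No inferential testing of safety data is planned (Protocol 12.3, SAP 9.2).

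**The concern.** A laboratory safety table should show how often a parameter moved out of range after treatment began. The SAP 8.4 proportion answers a different question: how many subjects had an abnormal value, whatever its history. Because the entry rule admits subjects with insignificant abnormalities, and sampling is non-fasting, some of those counted at Visits 9 and 13 will have been abnormal before the first application.

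Safety is a stated secondary objective. With no formal testing, readers will compare the percentages by eye. Pre-existing cases swell both arms, which shrinks the apparent ratio between them, and any chance difference in their number adds noise. The Visit 1 results that would remove both effects are already collected.

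**Working it through.** The documents give no laboratory rate, so there is no planned figure to reproduce. Every rate below is an assumption, shown over a range.

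**Inputs from the documents.** About 120 subjects randomized 1:1, so about 60 per arm. Protocol 9.3 lists 17 chemistry analytes and 15 numeric blood-count items (5 counts or indices, plus 5 differential cell types as both % and absolute), 32 in all. Samples are taken at Visits 1, 9 and 13.

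**Step 1: are pre-existing abnormalities likely?** Let a reference range leave a share q of healthy subjects outside it, and treat the 32 items as independent (a simplification, since differential items are correlated). Then P(at least one out of range) = 1 − (1 − q)^32.

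| q | At least one abnormal at Visit 1 | Expected per parameter, of 60 |
|---|---|---|
| 1% | 27.5% | 0.6 |
| 2.5% | 55.5% | 1.5 |
| 5% | 80.6% | 3.0 |

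Most subjects could have some abnormality at entry, while any one parameter has only a few cases per arm.

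**Step 2: dilution.** Let p0 be the share abnormal at Visit 1, r the share of those still or again abnormal on treatment, and v the rate of new abnormality among subjects in range at Visit 1. The SAP 8.4 proportion is then p0·r + (1 − p0)·v. Take v = 3% on vehicle and 10% on active, a true ratio of 10/3 = 3.33.

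| p0 | r | Vehicle | Active | Ratio |
|---|---|---|---|---|
| 2% | 0.5 | 3.9% | 10.8% | 2.74 |
| 5% | 0.5 | 5.3% | 12.0% | 2.24 |
| 5% | 1 | 7.9% | 14.5% | 1.85 |
| 10% | 1 | 12.7% | 19.0% | 1.50 |
| 20% | 1 | 22.4% | 28.0% | 1.25 |

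Over p0 = 2–20% and r = 0.5–1, pre-existing cases make up 25–89% of the vehicle count and 9–71% of the active count. The absolute difference shrinks much less. It equals (1 − p0) × 7 points, or 6.9 points at p0 = 2% and 5.6 at p0 = 20%. In counts for the last row, SAP 8.4 would show about 13.4 against 16.8 of 60. Among the 48 per arm in range at Visit 1, the new cases are 48 × 0.03 = 1.4 against 48 × 0.10 = 4.8.

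**Step 3: chance noise.** Suppose there are no new abnormalities and every Visit 1 abnormality persists. The SD of the difference between arms is √(2p(1 − p)/60): 4.0, 5.5 and 7.3 points at p = 5%, 10% and 20%. A gap of at least 10 points means at least 6 subjects of 60. With X and Y independent Binomial(60, p), the exact probability that |X − Y| ≥ 6, and the expected number among a rounded 30 parameters, are:

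| p abnormal | Probability | Expected of 30 |
|---|---|---|
| 2.5% | 0.0023 | 0.07 |
| 5% | 0.0219 | 0.7 |
| 10% | 0.0929 | 2.8 |
| 20% | 0.2084 | 6.3 |

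Persistence below 100% moves a parameter up this table: 10% abnormal with half persisting behaves like the 5% row.

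**The case against.** The plan has more protection than SAP 8.4 alone suggests.

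- **Visit 1 values are not counted themselves.** The limit to Visit 3 onward excludes them. This stands: only abnormalities that persist or recur at Visit 9 or 13 are mixed in.
- **Baseline laboratory data are summarised by arm (SAP 7.4).** A reader could see an imbalance at entry. This stands too, but two group summaries cannot show which subjects changed.
- **Clinically significant values are handled separately.** Protocol 9.3 bars randomization with one at Visit 1 and makes a later one an adverse event. This confines the mixing to values judged not significant. Those are also the values for which the out-of-range table is the main summary.
- **Subject-level listings are planned (16.2.8.2 to 16.2.8.5), and the mock tables are in a separate document that was not available for review.** The mock tables may show results by visit. Listings let a reader trace individuals, but they are not a summary by arm.
- **Large chance gaps need high rates.** In subjects required to be in good general health, 10% or 20% abnormal on every parameter is a demanding assumption. At 5% or below, fewer than one parameter in 30 would show a 10-point gap. The previous study of this drug also reported no clinically significant laboratory changes (Protocol 2.2).

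A reader might also infer that the SAP departs from the protocol by counting all abnormal values where Protocol 12.3 tabulates clinically relevant ones. The documents do not support that. SAP 9.2 carries the same sentence as Protocol 12.3, so both tabulations are planned. Only a matching title is missing from the table list.

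**Conclusion.** The point holds as a cheap improvement. As specified, the SAP 8.4 summary and its two tables cannot distinguish an insignificant abnormality carried over from Visit 1 from one that arose on treatment, and no other planned summary does so within subjects.

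It would be tempting to conclude that the tables are biased for or against the drug. They are not: randomization balances pre-existing cases in expectation. What remains is a diluted ratio and added noise in a descriptive comparison on which no test or decision rule depends.

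On the assumed 2–20% abnormal at Visit 1 and 50–100% persistence, a true ratio of 3.3 would appear as 2.7 to 1.25. With full persistence, between 0.07 and 6.3 of 30 parameters would show a chance gap of 10 points or more as the abnormal rate runs from 2.5% to 20%. These ranges are wide because the documents give no abnormality or persistence rates. The fact of mixing does not depend on them.

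**What to change.** In SAP 8.4 and Tables 14.3.4.1 and 14.3.4.2:

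1. For each parameter and arm, report the number and percentage of subjects newly low or newly high at Visit 9 or Visit 13. The denominator is subjects in range at Visit 1 with a result at the visit concerned.
2. Add a shift table by arm from Visit 1 (low, normal, high) to Visit 9 and to Visit 13. This keeps subjects who were abnormal at entry in view, including any who change direction.

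The tabulation of clinically relevant results already planned in SAP 9.2 can stay as it is, with a title added to the table list.

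The cost is one or two more table shells and a few sentences in the SAP. All the data are already scheduled for collection, and SAP Section 11 allows final tables to differ from the mock versions. The downside is a slightly smaller denominator for each parameter in the newly abnormal counts.

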8.5. Local Skin Reactions

Local Skin Reaction (LSR) scores will be summarized by frequency distributions for each symptom, by treatment group and visit. The proportion of subjects with with Severity > 0, and similarly for subjects with Severity > 1 will be presented for each symptom, by visit.

9. STATISTICAL ANALYSIS METHODS

9.1. Statistical Analysis of Efficacy Data

Primary and secondary efficacy analyses will be performed on the Per-Protocol population, defined as all randomized subjects who missed no more than 3 treatment visits, completed Visit 10 (and Visit 13 for purposes of the Visit 13 analysis), and who have not had a major protocol violation over that time period including the use of a clinically relevant quantity of a prohibited medication as determined by the study Medical Monitor. No missing data imputation will be used for these analyses.

Visit 10 is considered to be the primary efficacy endpoint. In addition, some analyses will also be conducted at earlier and subsequent visits, and treated as exploratory analyses. Some sensitivity efficacy analyses may also be re-performed on the Intent to Treat population, defined as those randomized subjects who have at least one post-baseline visit with required efficacy data collection and who completed Visit 10 with required collection of efficacy data. For those analyses, missing efficacy data for intermediate visits may be imputed using the last observation carried forward (LOCF) procedure. A determination as to the performance of such analyses using the Intent to Treat population will be based on the number and pattern of visits missed by randomized subjects. Exploratory analyses using models specified below may also be performed for separate sub-groups, depending on enrollment outcomes.

For all analyses, two-tail alpha will be set to 0.05 unless otherwise specified, with no adjustment for multiple comparisons. ANOVAs and ANCOVAs will include Site in the model only if doing so improves the sensitivity of the model for comparing treatment groups.

After the last randomized subject has completed Visit 10 the efficacy data captured to date in the database will be validated, locked through Visit 10 and unblinded for the purpose of analyzing efficacy data through Visit 10. Those analyses are not considered to be interim analyses as the results will be final. Data will continue to be collected through Visit 13 for all subjects, and the full database will subsequently be locked for efficacy analysis (including durability of response) beyond Visit 10, and for the analysis of safety and all other clinical data.

The primary efficacy analysis will be a comparison between treatment groups based on the mean change in Target Wart PWA from Baseline (Visit 2) to Visit 10, using Analysis of Covariance with Baseline PWA as the covariate.

Secondary efficacy analyses will include comparisons between treatment groups based on the following: the proportion of subjects with the Target Wart Clear (PWA = 0) at Visit 10 using a one-tail Fisher's Exact Test; the proportion of subjects with the Target Wart Clear or Near-Clear (PWA = 0 or 1) at Visit 10 using a one-tail Fisher's Exact Test; the proportion of subjects with all treated warts Clear at Visit 10 using a Cochran-Mantel-Haenszel test stratified by number of treated warts; the proportion of subjects with all treated warts Clear or Near-Clear at Visit 10 using a Cochran-Mantel-Haenszel test stratified by number of treated warts; the proportion of subjects with all treated warts Clear or Near-Clear at Visit 10 using a Cochran-Mantel-Haenszel test stratified by number of treated warts; the mean of persubject percentages of treated warts that are Clear at Visit 10 using Analysis of Variance; the

mean of per-subject percentages of treated warts that are Clear or Near-Clear at Visit 10 using Analysis of Variance; and the mean of per-subject percent change from baseline PWA for treated warts using Analysis of Variance.

Durability of response in the Active treatment group will be evaluated by calculating the proportion of those treated warts achieving a PWA status of Clear at Visit 10 which continue to maintain a PWA status of Clear at Visit 13. This analysis will be performed separately for Target Warts, and for all treated warts. The 95% confidence limits around the calculated proportions will also be calculated in order to estimate the population lower limit value of the observed sample proportions.

Exploratory analyses may be conducted using a subset of the above analysis models, based on lesion sub-groups including body location, age, time to clearance, and also the following baseline wart classification: warts that are determined to be treatment-naive vs. recalcitrant.

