⁵Prior medications/therapies will be collected for a time-period of 13 days prior to Visit 2. Refer to Section 7.8 for a list of permitted and restricted concomitant medications.

⁶A complete blood count (including hematocrit, hemoglobin, platelet count, red blood cell count and morphology, white blood cell count and differential (absolute and %) including basophils, eosinophils, lymphocytes, monocytes and neutrophils and a clinical chemistry panel including albumin, alkaline phosphatase, alanine aminotransferase (ALT), aspartate aminotransferase (AST), blood urea nitrogen (BUN), bicarbonate, calcium, chloride, creatinine, glucose, lactate dehydrogenase (LDH), phosphorus, potassium, sodium, total bilirubin, total protein, and uric acid.

⁷ Woman of child bearing potential will be required to have a urine pregnancy test at Visit 1, at Visit 2 prior to randomization, Visit 9 and Visit 13.

⁸The treating investigator will identify 1 Target Wart and up to 3 additional Non-Target Warts on the trunk and extremities.

⁹ The investigator will use the Physician Wart Assessment (PWA) to assess each Target and Non-Target Warts. The investigator must assess the Target and Non-Target Warts prior to application of the study medication at Visit 2-Visit 9. In order to be eligible for randomization at Visit 2, the subject must have a PWA grade ≥ 2 .

¹⁰ The investigator will measure the dimensions (longest diameter and thickness) of the Target and Non-Target Warts at Visit 1 and prior to randomization at Visit 2. In order for the subject to be randomized at Visit 2 each Target and Non-Target Wart must have the specific dimensions outlined in Section 8.1. At Visits 3-13 the investigator will measure the diameter of each Target and Non-Target Wart.

¹¹ At Visits 1, Visit 2 (prior to study medication application), Visit 4 prior to study medication application, Visit 9, Visit 10 and at Visit 13, a qualified investigational center staff member will take a photograph of each Target and Non-Target Wart using the Aclaris supplied camera. All photographs will be sent to a central imaging laboratory.

¹² Subjects will be randomized at Visit 2 prior to application of study medication. Investigational study staff will re-confirm subject eligibility prior to randomization.

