8.3. Physician's Wart Assessment (PWA)

The Physician's Wart Assessment (PWA) is the Investigator's assessment of the severity of each Target and Non-Target Wart at a particular time point. The Investigator should NOT refer to any other assessments to assist with this evaluation. This evaluation IS NOT a comparison with the PWA at any other visit.

At every study visit, the Investigator will assess the Target and Non-Target Warts and report the one integer that best describes the Target and Non-Target Wart severity using the following scale. At any visit where a study medication treatment is performed, the PWA must be completed prior to the treatment.

	Physician's Wart Assessment						
Grade	Descriptor						
0	Clear: No visible wart. No further treatment is indicated						
1	Near Clear: A visible wart that is less than 3mm in maximal diameter (or length)						
2	A visible wart \geq 3mm and <6 mm in maximal diameter (or length)						
3	A visible wart \geq 6mm in maximal diameter (or length)						

At Visit 1 for the subject to be enrolled and at Visit 2 for the subject to be randomized each Target and Non-Target Wart must have a PWA grade ≥ 2 .

At Visits 3-9, Target and Non-Target Warts must have a PWA > 0 to be retreated. If the Investigator cannot assess the PWA for a Target or Non-Target Wart (*e.g.*, the Target /Non-Target Wart cannot be visualized because of an LSR such as edema, scabbing, etc.) she/he must report the reason in the subject's CRFs. The Target/Non-Target Wart must not be retreated at that visit, and the subject should be seen at the next scheduled visit.

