5. ASSESSMENTS OF CLINICAL EFFICACY

5.1. Target and Non-Target Wart Identification

At Visit 1, the investigator will identify one Target Wart and up to 3 additional Non-Target Warts on the trunk or extremities for each subject for treatment and evaluation.

For this study, the trunk and extremities are defined as:

- The front and back of the torso from the clavicle to the hips, including the buttocks and excluding the genitals and anus
- The arms from the shoulder to the fingertips, excluding periungual and subungual areas
- The legs from the hip to the ankles (including the dorsal side of the foot).

At Visit 1, each Target and Non-Target Wart must:

- Have a longest axis that is ≥ 3 mm and ≤ 8 mm
- Have a thickness ≤ 3 mm
- Be a discrete lesion
- Be, when centered in the circular cutout of the provided template, the only common wart present (Refer to Figure 1)
- Not be periungual, subungual, genital, anal, mosaic, plantar, flat or filiform.
- Not be covered with hair which, in the Investigator's opinion, would interfere with the study medication treatments or the study evaluations
- Not be in an area that may be occluded (*e.g.*, by clothing or footwear or in a skin fold).

Record the location of the Target and Non-Target Wart on the body charts in the CRFs indicating landmarks and distances to assist with confirming the location of the Target and Non-Target Warts at subsequent visits.

At Visit 1, the Investigator and an investigational staff member will identify each Target and Non-Target Wart by placing 2 identification (ID) stickers approximately 180 degrees opposite each other with the identified wart in the center of the area outlined by the provided circular template (diagram not to scale):

Figure 1Target/Non-Target Wart Identification

At Visits 2-13, an investigational staff member (other than the evaluating investigator) will confirm the location of each Target/Non-Target Wart using an appropriate combination of the Visit 1 hard-copy reference prints, Visit 2 photographs and the body charts. The staff member will identify the Target/Non-Target Warts by placing 2 appropriately colored ID stickers, with the Target/Non-Target Wart number written on one sticker, approximately 180 degrees opposite each other with the identified wart in the center of area outlined by the provided circular template.

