5.3. Physician's Wart Assessment (PWA)

The Physician's Wart Assessment (PWA) is the Investigator's assessment of the severity of each Target and Non-Target Wart at a particular time point. The Investigator should NOT refer to any other assessments to assist with this evaluation. This evaluation IS NOT a comparison with the PWA at any other visit.

At every study visit, the Investigator will assess the Target and Non-Target Warts and report the one integer that best describes the Target and Non-Target Wart severity using the following scale. At any visit where a study medication treatment is performed, the PWA must be completed prior to the treatment.

	Physician's Wart Assessment
Grade	Descriptor
0	Clear: No visible wart. No further treatment is indicated
1	Near Clear: A visible wart that is less than 3mm in maximal diameter (or length)
2	A visible wart \geq 3mm and <6 mm in maximal diameter (or length)
3	A visible wart \geq 6mm in maximal diameter (or length)

At Visit 1 for the subject to be enrolled and at Visit 2 for the subject to be randomized each Target and Non-Target Wart must have a PWA grade ≥ 2 .

At Visits 3-9, Target and Non-Target Warts must have a PWA > 0 to be retreated. If the Investigator cannot assess the PWA for a Target or Non-Target Wart (*e.g.*, the Target /Non-Target Wart cannot be visualized because of an LSR such as edema, scabbing, etc.) she/he must report the reason in the subject's CRFs. The Target/Non-Target Wart must not be retreated at that visit, and the subject should be seen at the next scheduled visit.

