Table 14.3.5.7	Mean and Mean Change from Pre-Treatment in Vital Signs: Systolic Blood Pressure (mm Hg)
Table 14.3.5.8	Mean and Mean Change from Pre-Treatment in Vital signs: Diastolic Blood Pressure (mm Hg)
Table 14.3.5.9	Mean and Mean Change from Pre-Treatment in Vital signs: Pulse Rate (beats/min)
Table 14.3.5.10	Mean and Mean Change from Pre-Treatment in Vital signs: Respiratory Rate (breaths/min)
Table 14.3.5.11	Mean and Mean Change from Pre-Treatment in Vital signs: Body Temperature (deg F)
Table 14.3.5.12	Concomitant Medications – Safety Population

SUBJECT DATA LISTINGS

16.2.1	Discontinued Subjects
Listing 16.2.1.1	Disposition of Subjects
16.2.2	Protocol Deviations
Listing 16.2.2.1	Protocol Deviations/Violations
16.2.4	Demographic Data
Listing 16.2.4.1	Demographic Information and Informed Consent
Listing 16.2.4.2	Medical History and Concomitant Conditions
Listing 16.2.4.3	Prior and Concomitant Medications
16.2.5	Compliance Data [See L6,7,7.1]
Listing 16.2.5.1	Study Medication Inventory
Listing 16.2.5.2	Randomization and Study Medication Application
16.2.6	Efficacy Data
Listing 16.2.6.1	Treated Wart Assessments: PWA Values by Treatment and Visit
Listing 16.2.6.2	Treated Wart Assessments: PWA responders with PWA Clear ($PLA = 0$)
	at Visit 10, by Treatment and Visit
Listing 16.2.6.4	Treated Wart Assessments: PWA Responders with PWA <= 1 at Visit 10, by Treatment and Visit
Listing 16.2.6.5	Treated Wart Dimensions – Length of Longest Axis, Values by
	Treatment
16.2.7	Adverse Event Listings
Listing 16.2.7.1	Mapping of MedDRA System Organ Class, MedDRA Preferred Term, and CRF Verbatim Terms
Listing 16.2.7.2	Treatment Emergent Adverse Events
Listing 16.2.7.2.1	Treatment Emergent Serious Adverse Events
Listing 16.2.7.3	Treatment Emergent Adverse Events Classified as Cutaneous by Investigator
16.2.8	Laboratory Listings
Listing 16.2.8.1	Female Pregnancy Tests
Listing 16.2.8.2	Lab Battery Name: Chemistry
Listing 16.2.8.3	Lab Battery Name: Chemistry: Results Outside Normal Range
Listing 16.2.8.4	Lab Battery Name: Hematology & Differentials
Listing 16.2.8.5	Lab Battery Name: Hematology & Differentials: Results Outside Normal Range

Page 31 of 32 Date: 21 November 2017

16.2.9	Other Listings
Listing 16.2.9.1	Treated Wart Local Skin Reactions (Evaluated by Subject), Values by
	Symptom, Treatment, and Visit
Listing 16.2.9.2	Treated Wart Local Skin Reactions (Evaluated by Investigator), Values
	by Symptom, Treatment and Visit
Listing 16.2.9.3	Vital Signs

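### Visit 2 wart diameter in mm, already measured, could join baseline PWA in the primary ANCOVA for a probably modest gain in precision; the planned analysis is valid without it

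*SAP*

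**What the plan says.** SAP 9.1 and Protocol 12.2 agree on the primary comparison: mean change in Target Wart PWA between Visit 2 and Visit 10, "using Analysis of Covariance with Baseline PWA as the covariate". One further term is possible: "ANOVAs and ANCOVAs will include Site in the model only if doing so improves the sensitivity of the model". No other covariate is named.

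Four other places bear on what that covariate can do.

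- SAP 5.3 (and Protocol 8.3) sets the entry floor: "each Target and Non-Target Wart must have a PWA grade ≥ 2". The scale ends at 3. Grades 1, 2 and 3 are bands of largest diameter: under 3 mm, 3 to under 6 mm, and 6 mm or more.
- SAP 5.1 (and Protocol 8.1) limits the size of each wart: "Have a longest axis that is ≥ 3 mm and ≤ 8 mm".
- Footnote 10 to Table 1 in Protocol section 6 has the investigator "measure the dimensions (longest diameter and thickness) of the Target and Non-Target Warts" at Visit 1 and again before randomization at Visit 2.
- In SAP section 11, diameter appears only in Listing 16.2.6.5 ("Length of Longest Axis"). No titled efficacy table and no model uses it.

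Protocol 12.1 and SAP 7.1 expect more than 90% power. They give no treatment difference, SD or correlation.

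**The concern.** The outcome moves only when a wart falls below 6 mm, falls below 3 mm, or clears. How far a wart starts from those cut-points may therefore predict whether its grade changes. Baseline PWA does not carry that information within a grade: warts of 3.2 mm and 5.8 mm both enter as grade 2, and if warts shrink by a millimetre or two they have different chances of reaching grade 1. Diameter can separate them, and it is recorded before treatment is assigned.

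What is at stake is the residual variance of the primary comparison. If diameter explains part of the variation in PWA change that baseline PWA leaves over, the planned standard error is larger than it needs to be.

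**Working it through.** **1. The stated power.** It cannot be reproduced, because no effect size or SD is given. It can be back-solved. With about 120 evaluable subjects at 1:1 (60 per arm) and two-sided 0.05, the smallest standardized effect giving 90% power is (1.960 + 1.2816) × √(2/60) = 0.592. Power is 90.8% at 0.6 and 97.0% at 0.7, but 78.2% at 0.5.

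**2. What baseline PWA already captures.** Assume diameters uniform on 3 to 8 mm.

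- Total variance is 25/12 = 2.083, with mean 5.5.
- Grade 2 holds 60% of warts (mean 4.5) and grade 3 holds 40% (mean 7.0).
- Between-grade variance is 0.6 × 1.0² + 0.4 × 1.5² = 1.50.
- 1.50 / 2.083 = 72%.

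The two-valued score thus already holds most of the size information, which limits what diameter can add.

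**3. Gain as a function of the unknown correlation.** Let r be the partial correlation of baseline diameter with PWA change, given treatment and baseline PWA. Residual degrees of freedom fall from 120 − 3 = 117 to 116. The variance ratio is f = (1 − r²) × 117/116, relative efficiency is 1/f, and power is Φ(3.2415/√f − 1.960), starting from 90%. Every r here is an assumption.

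| r | SE ratio √f | Relative efficiency 1/f | Power |
|---|---|---|---|
| 0 | 1.004 | 0.99 | 89.8% |
| 0.1 | 0.999 | 1.00 | 90.0% |
| 0.2 | 0.984 | 1.03 | 90.9% |
| 0.3 | 0.958 | 1.09 | 92.3% |
| 0.4 | 0.920 | 1.18 | 94.1% |
| 0.5 | 0.870 | 1.32 | 96.1% |

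At r = 0 the loss is about 0.25 points from 90% power. From 80% power it is about 0.34 points (80.0% to 79.66%).

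**4. Plausible values of r.** Simulation with 60 per arm, under assumed response models:

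- *Shrinkage plus some clearing.* Mean shrinkage was 1 mm on vehicle and 2 mm on active with SD 1 or 2 mm (in the proportional models, the drawn shrinkage divided by 5, as a fraction of baseline diameter). Clearing was 5% v 25%. Baseline diameters were uniform or skewed small. Partial r was 0.16 to 0.35. For absolute shrinkage the SE ratio was 0.945 to 0.981, so relative efficiency was 1/0.945² = 1.12 down to 1/0.981² = 1.04. For proportional shrinkage it was 0.971 to 0.996, so 1.06 down to 1.01. Rounding diameter to whole mm reduced the gain in all eight paired comparisons.
- *Adding measurement error.* In a separate run, whole-mm rounding with 0.5 mm error took relative efficiency from 1.10 to 1.05 (absolute) and from 1.05 to 1.03 (proportional).
- *All-or-none clearing unrelated to size (40% v 10%).* Relative efficiency was 0.99, with power 97.3% under both models. This follows from the scale: a cleared wart changes by exactly its baseline grade and an uncleared wart by zero, so diameter adds nothing once PWA is known.
- *A further run* gave 0.98 to 0.99 for all-or-none clearing, 1.01 to 1.05 for proportional or mixed shrinkage, and 1.09 to 1.15 for absolute shrinkage.

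**5. Translation.** A relative efficiency of 1.15 is worth 120 × 1.15 = 138 subjects, or 18 more. 1.05 is worth 126, or 6 more. 0.99 is worth 118.8, or about 1 fewer. At 1.15, √f = √(1/1.15) = 0.9325 and power is Φ(3.2415/0.9325 − 1.960) = Φ(1.516) = 93.5%.

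**6. Validity.** Simulated type I error with diameter in the model was 4.4% to 5.5% against a nominal 5%.

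**The case against.** The strongest reply is that nothing is wrong. ANCOVA on the outcome's own baseline is standard, it is pre-specified, and the two documents agree on it. The estimate is unbiased and the error rate holds. Stated power already exceeds 90%, and moving it by a few points is unlikely to change the trial's conclusion. Diameter is read by investigators at about 15 centres, so it carries error. Every figure for the gain rests on response models that the documents do not supply.

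Most of that stands, and it limits the point. A reader might infer any of the following, and the documents support none of them:

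- *The planned test is biased or invalid.* Leaving out a prognostic covariate in a randomized comparison costs precision only.
- *The gain is guaranteed and costs nothing.* If warts mostly either clear or stay as they are, there is no gain and one degree of freedom is spent. A few per cent is not a floor.
- *Warts of 3.2 mm and 5.8 mm necessarily differ greatly in their chance of dropping a grade.* That depends on how warts shrink, which the documents do not describe.
- *The model can adjust for nothing but a two-valued score.* Site may enter as well, although it does not measure wart size.

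The appeal to existing power is weaker. The margin above 90% cannot be checked, since neither document gives the effect or SD behind it, and at a standardized effect of 0.5 power would be 78.2%.

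**Conclusion.** The point holds as an efficiency improvement. The only pre-specified baseline severity covariate is in effect a 6 mm split, while a finer pre-randomization measurement of the same dimension goes unused in the model. Adding it would probably improve precision modestly. Relative efficiency runs from about 0.99 to about 1.15, and rounding or measurement error pulls the upper end down. The worst case costs roughly 0.2 to 0.4 points of power; the best adds about 3.5 points to 90%.

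The range depends on assumed diameter distributions, shrinkage patterns and clearing rates. The direction is likely but not certain. The planned analysis remains valid if it is left unchanged.

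**What to change.** Before the Visit 10 unblinding, state in Protocol 12.2 and SAP 9.1 that:

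- the primary ANCOVA of change in Target Wart PWA includes treatment, baseline PWA and Visit 2 Target Wart longest diameter in mm;
- this model alone determines the primary conclusion;
- the model with baseline PWA only is a supportive sensitivity analysis, so a disagreement near p = 0.05 does not reopen the primary result.

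Two details belong in the same edit. Say what is used if the Visit 2 diameter is missing; the Visit 1 measurement is available and also precedes randomization. Settle in advance whether Site is in the model, because a term chosen on the data would leave the primary model unfixed.

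The diameter covariate costs one degree of freedom (117 to 116 with 120 subjects) and a short change to each document. It needs no new data.
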